6.5 Missing Values, Abnormal Value and Outliers

Data entry error or non-reasonable values will be cleaned before data analysis. Imputation of missing data will be only applied for sensitivity analysis. And strategies are as follows:

The missing paired YSI-SG is caused from the following cases but not limited to:

- Missing FST-YSI
- FST-YSI with deletion flag (from protocol deviations collected by CRF)
- · Existing FST-YSI value without paired SG point

Three imputation methods will be used for sensitivity analysis are as follows:

(1) Worst Case

- 1) 20/20% agreement rate: The missing paired YSI-SG will be filled with a 20/20% agreement of "No".
- 2) Zone of Clarke and Consensus Error Grid: The missing paired YSI-SG will be filled with a "Zone E".
 - 3) ARD (%): The missing paired YSI-SG will be filled with a maximum value from the study data.

(2) Best Case

- 1) 20/20% agreement rate: The missing paired YSI-SG will be filled with a 20/20% agreement of "Yes".
- 2) Zone of Clarke and Consensus Error Grid: The missing paired YSI-SG will be filled with a "Zone A".
 - 3) ARD (%): The missing paired YSI-SG will be filled with a minimum value from the study data.

(3) Randomly Pick from the Same Subject

- 1) The missing paired YSI-SG will be filled with a 20/20% agreement of random selection from the same subject.
- 2) The missing paired YSI-SG will be filled with a Zone of Clarke and Consensus Error Grid of random selection from the same subject.
- 3) The missing paired YSI-SG will be filled with an ARD (%) of random selection from the same subject.

For the dates of adverse events and medications collected during the trial, if the day or month or year is filled with "UK" or "NA", they will not be processed.

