7.7 Sensitivity analyses of primary endpoints

Sensitivity analyses will be performed on the FAS#2.

(1) Missing data

To account for the effect of both missing data (e.g. missing FST-YSI^{TM*}, existing FST-YSI^{TM*} value without paired SG point, etc.), and FST-YSI^{TM*} with deletion flag (from protocol deviations collected by CRF) for primary endpoints evaluation, relevant sensitivity analyses for primary endpoints will also be provided.

In these analyses, the missing paired YSI-SG will be handled based on worst case, best case and randomly pick from the same subject methods, respectively. (See section 6.5). The 20/20% agreement rate, a mean rate in Zone A+B of Clarke and Consensus Error Grid based on measurement level will be analyzed after missing data being handled according to above different methods in sensitivity analysis.

(2) Site Effect

Investigative site effect will be evaluated using the generalized estimation equation (GEE) for 20/20% agreement rate, a mean rate in Zone A+B of Clarke and Consensus Error Grid and the linear regression

model for MARD. If site effect is detected, sensitivity analysis will be performed using the random-effects models to obtain combined effect for endpoints. If the random-effects model is not feasible then the estimation of fixed-effects model will be provided. Inverse variance method (weight=1/variance of site estimate) will be used in the analysis.

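### For 1a to 1c, the random-pick sensitivity analysis counts imputed pairs as observed data, so its confidence limits are too narrow

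*SAP*

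**What the plan says.** SAP 6.5 confines filling to secondary use: "Imputation of missing data will be only applied for sensitivity analysis". It names three methods: worst case, best case and a random pick, headed "3) Randomly Pick from the Same Subject". For 1a the random pick reads: "The missing paired YSI-SG will be filled with a 20/20% agreement of random selection from the same subject". The error-grid zones are treated the same way, and there is a matching rule for the relative difference: "The missing paired YSI-SG will be filled with an ARD (%) of random selection from the same subject".

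SAP 7.7 applies "worst case, best case and randomly pick from the same subject methods" on FAS#2. It says that the three rates (1a, 1b, 1c) "based on measurement level will be analyzed after missing data being handled according to above different methods in sensitivity analysis". Neither section states how many draws are made, what seed is used, how draws would be combined, or any allowance in the variance for imputed values.

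SAP 7.6 sets the primary analysis: observed pairs only, normal-approximation and Clopper-Pearson limits at measurement level for 1a to 1c, and a one-sample t test at subject level for 1d. SAP 6.9 sets one-sided 0.025.

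**The concern.** A filled pair carries no new information; it repeats a result already seen in that subject. If it is entered once and counted in the denominator, two things happen together. The estimate gains noise from the draw, and the stated standard error shrinks because N has gone back up. For the same observed rate, the check on missing data then reports a tighter limit than the primary analysis that it is meant to test.

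The result also turns on one unspecified draw. SAP section 8 allows validation by independent programming, and without a seed two correct programs would give different numbers.

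The random pick is the only scenario between the two extremes. The best case cannot overturn a pass. At the design rates the worst case fails at a small missing share (step 4 below). A reader who wants a moderate view of missing data has only this analysis.

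**Working it through.** **Inputs.** From SAP 6.2: 60 subjects, at least 20 pairs each, 1,200 pairs; 1a at 0.65 against 0.60; 1b and 1c at 0.95 against 0.90. From SAP 6.9: one-sided 0.025, so 1.96. The missing share f and the within-subject correlation (ICC) are assumptions; the documents give neither.

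**1. The plan's own figures.** The SAP's formula for 1a gives n = [1.96 × √(0.60 × 0.40) + 0.845 × √(0.65 × 0.35)]² / 0.05² = 743.4 pairs. For 1b and 1c it gives 238.5. With 1,200 pairs, power is 94.7% for 1a and above 99.9% for 1b and 1c, so the claims of more than 80% reproduce under the SAP's independence assumption.

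**2. Variance after one fill, independent pairs.** Of N pairs, (1 − f)N are observed and fN are drawn from them.

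- True variance: p(1 − p) × [1/((1 − f)N) + f/N]
- Stated variance, all N treated as observed: p(1 − p)/N
- Ratio: 1/(1 − f) + f

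| f | variance ratio | SE ratio | one-sided error, P(Z > 1.96 / SE ratio) |
|---|---|---|---|
| 5% | 1.103 | 1.05 | 3.1% |
| 10% | 1.211 | 1.10 | 3.7% |
| 20% | 1.450 | 1.20 | 5.2% |

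Simulation of 60 × 20 independent pairs at a true rate of 60% gave about 3.4% at f = 5%, 4.1% to 4.3% at 10%, and 5.4% to 5.9% at 20%. Observed pairs alone gave 2.5% to 2.8%. At a true rate of 90%, the observed-pair limit is itself slightly liberal (3.4% and 3.3% at f = 10% and 20%); the fill gave 4.9% and 6.9%.

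**3. Lower limits at the design rates (N = 1,200).**

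| | observed pairs | random pick as written | random pick with imputation variance |
|---|---|---|---|
| 65%, f = 10% | 0.6216 | 0.6230 | 0.6203 |
| 65%, f = 20% | 0.6198 | 0.6230 | 0.6175 |
| 95%, f = 10% | 0.9370 | 0.9377 | 0.9364 |
| 95%, f = 20% | 0.9362 | 0.9377 | 0.9352 |

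As written, the limit does not move with f. All limits stay above 0.60 and 0.90.

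**4. Worst case for comparison.** The filled rate is 0.65(1 − f). Its lower limit reaches 0.60 when the rate is about 0.627, so f = 1 − 0.627/0.65, about 3.5%. The same step for 0.95 against 0.90 gives about 3.6%.

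**5. What the random pick can detect.** Take a subject with n pairs, of which o are observed and y agree. Averaged over draws, the filled rate is [y + (n − o) × y/o]/n = y/o. The method therefore restores each subject's full weight but leaves each subject's own rate unchanged. In a simulation with missing pairs concentrated in poor performers (assumed ICC 0.2, f = 20%, true rate 60%), observed pairs averaged 64.2% and the random pick 60.0%. If instead the missing pairs are worse than the observed pairs of the same subject, the method cannot show it. One possible source is in SAP 6.6.1, where sensor readings outside 40 to 400 mg/dL become null in the column used for accuracy. On a natural reading these are YSI values without a paired sensor value, and they would be filled from in-range pairs.

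**6. MARD (1d).** The t test counts subjects, so filling does not raise n. Simulated error at the 20% threshold, with an assumed within-subject spread, was 2.1% both ways at f = 10% and 2.5% both ways at f = 20%.

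**7. Does combining draws repair it?** Simulated error at a true rate of 60%:

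- Repeated fills, Rubin's rules, binomial variance: about 2.5% to 2.9% at ICC 0, but about 11% to 20% at ICC 0.1 to 0.2.
- Variance taken over subjects: about 2% to 4%.

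**The case against.** The strongest reply is that nothing depends on this analysis. Pass/fail uses observed pairs, and SAP 7.7 states no threshold test for the filled data. That one fill is made, and that limits use the full N, is inferred from silence; the mock tables are in a separate appendix. At the design rates the limit for 1a changes by 0.0027 (0.6230 to 0.6203) at 10% missing and 0.0055 at 20%. All of this stands, and it keeps the point minor. It does not remove the fault, because analysing filled data at measurement level without a variance rule leads to these limits.

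A second reply is that within-subject correlation matters more. With assumed ICC 0.1 to 0.2 and f of 10% to 20%, observed pairs already give 11% to 18% error, and the random pick 14% to 20%. That is correct. It is a wider issue that also touches the primary analysis, and it determines the form of the fix.

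A reader might go further and infer that the random pick can never challenge the primary result. The documents do not support this. Step 5 shows that it lowers the rate when poor performers lose more pairs; in that scenario its limit was below the primary limit in every run. Even with missingness unrelated to the subject, it was lower in about 29% to 37% of runs. The worst-case fill in the same section is also a severe challenge.

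**Conclusion.** The point holds for 1a, 1b and 1c. On the natural reading of SAP 6.5(3) and 7.7, the random pick is one fill with imputed pairs counted as observed. With independent pairs its standard error is too small by a factor of about 1.05, 1.10 and 1.20 at an assumed 5%, 10% and 20% missing, and the one-sided error is about 3% to 6% instead of 2.5%. The result depends on one draw. The method reflects missingness that differs between subjects, but not missing pairs that are worse than the same subject's observed pairs.

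Two wider conclusions should not be drawn. The narrowing does not reach MARD, which is tested by subject; the SAP 7.7 sentence on analysing filled data names only the three rates. Nor is the trial's own error rate changed, since imputation does not enter pass/fail. This is a small, inexpensive repair to a sensitivity analysis.

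**What to change.** In SAP 6.5(3) and 7.7:

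- State that the within-subject draw is repeated many times (for example 200) with a fixed, recorded seed, and how the results are combined.
- Compute the limit with a subject-level (clustered) variance. One simple form averages each subject's filled rate over the draws and takes the variance across subjects. Rubin's rules with the binomial variance would not be enough, as step 7 shows.
- State that the method assumes a subject's missing pairs resemble that subject's observed pairs. A tipping-point analysis between the random pick and the worst case would cover departures from this.
- Say whether the relative-difference fill defined in 6.5 is analysed for 1d.

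The cost is a loop and a combining step in the code, and somewhat wider sensitivity limits. No new data are needed and the pass/fail rule does not change.

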6.6 General Considerations for Data Analysis

6.6.1 Data Collection

Analysis data source: The analysis of primary endpoints, other descriptive endpoints and simulation alert calculation will be based on both Oracle Remote Data Capture (RDC) database and external device dataset (collected sensor glucose data). The detailed specification of variables from external device data are as following:

- SG: Raw Sensor Glucose Reading
- PSGV: Predicted Sensor Glucose Reading
- SBG: Sensor Blood Glucose (values below 40 display as 40, values above 400 display as 400) elaborated below
- ROC: Rate of Change of SG
- ISIG: Interstitial Signal
- FORCALBG: Used in Calibration

The value "511" in the SG and PSGV column indicates "null". The SBG column will display saturated values of 40 if the reading was displayed as "Low" (i.e. if SG < 40 mg/dL) or 400 if the reading was "High" (i.e. if SG > 400 mg/dL) while the SG column will display 511. SG value of 40 is indicated when SG and SBG columns are equal to 40, and same for 400. SG column is used to generate the numerical calculation for sensor performance. SBG is used for alert analysis and sensor life analysis. PSGV and ROC columns are used for alert analysis.

In addition, primary endpoints, other descriptive endpoints, and functional sensor life time will be based on real-time data collected from primary sensor. Precision analysis will be based on data collected from both sensors.

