6.6.2 Pairing Scheme

- 1) All YSI^{TM*} collected will be presented. Descriptive analyses will include all YSI^{TM*} values, such as those less than (<) 40 mg/dL, or greater than (>) 400 mg/dL as long as GuardianTM Sensor (3) values are greater than or equal to (≥) 40 mg/dL or less than or equal to (≤) 400 mg/dL.
- 2) Reference glucose values (YSI^{TM*} values) will be paired with the closest GuardianTM Sensor (3) value between [0, 5) minutes.
- 3) The primary Guardian™ Sensor (3) will be used as a reference for precision analysis and the pairing scheme will be [0, 5) minutes.

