7.6 Primary Endpoints

Detailed analyses for four primary endpoints are as following:

- 1a) For the 20/20% agreement rate analysis, the analyses based on measurement level will be provided. Both the approximate normal distribution method and Clopper-Pearson method will be used to estimate primary endpoint based on measurement level. The 97.5% lower confidence limit of the agreement rate will be tested against corresponding threshold.
- 1b) Sensor values from primary sensor will be compared to YSI^{TM*} plasma glucose values during YSI^{TM*} FSTs. A mean rate in Zone A+B of Consensus Error Grid between Guardian Sensor (3) values and YSI^{TM*} plasma glucose values during YSI^{TM*} FST days.
- 1c) Sensor values from primary sensor will be compared to YSI^{TM*} plasma glucose values during YSI^{TM*} FSTs. A mean rate in Zone A+B of Clarke Error Grid between Guardian Sensor (3) values and

YSITM* plasma glucose values during YSITM* FST days.

1d) Sensor values from primary sensor will be compared to YSI^{TM*} plasma glucose values during YSI^{TM*} FSTs. A mean absolute relative difference (MARD) between Guardian Sensor (3) values and YSI^{TM*} plasma glucose values during YSI^{TM*} FST days.

At 1b) and 1c) evaluation criteria, both the approximate normal distribution method and Clopper-Pearson method will be used to analysis primary endpoint based on measurement level. The 97.5% lower confidence limit of the mean rate in Zone A+B of Consensus Error Grid, and the mean rate in Zone A+B of Clarke Error Grid will be tested against corresponding threshold, respectively.

At 1d) evaluation criteria, one sample T test will be used based on subject level and the 97.5% upper confidence limit of the MARD will be tested against corresponding threshold.

The study will be considered as a success only when the four evaluation criteria (1a), 1b), 1c), and 1d)) meet the pre-defined thresholds.

The analysis of primary endpoint will be performed on both the FAS^{#2} and PPS; and will be based on the available paired data only according to pairing scheme after considering YSI^{TM*} retention and sensor data retention principle.

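### Readings displayed as Low or High are null in the SG column and leave all four primary endpoints, even where they are certain misses

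*SAP*

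**What the plan says.** SAP 6.6.1 defines two sensor columns.

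- **SG** holds the raw reading, with a null code: "The value '511' in the SG and PSGV column indicates 'null". For an out-of-range display the saturated value goes elsewhere. On the high side, SBG shows 400 "if the reading was 'High' (i.e. if SG > 400 mg/dL) while the SG column will display 511"; the low side works the same way with 40.
- **SBG** keeps the 40 or 400. Its use is limited: "SBG is used for alert analysis and sensor life analysis".

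Accuracy comes from the first column: "SG column is used to generate the numerical calculation for sensor performance". SAP 7.6 says that the primary analysis "will be based on the available paired data only according to pairing scheme", and SAP 6.5 confines imputation to sensitivity analyses. One of the missing-pair cases in SAP 6.5 is "Existing FST-YSI value without paired SG point", which fits a null SG. The worst case fills such a pair with No, Zone E and the maximum ARD. The best case fills it with Yes, Zone A and the minimum ARD.

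SAP 6.6.2 (and Protocol 14.8.2) admits YSI values of any size as long as sensor "values are greater than or equal to (≥) 40 mg/dL or less than or equal to (≤) 400 mg/dL". SAP 6.6.4 says that all collected sensor glucose data will be analysed, which sits badly with 6.6.1.

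**The concern.** A reading displayed as Low or High is not missing. The device gave the user a result, and the plan relies on that result for its alert analysis. The true sensor value is known to lie below 40 or above 400, and beside many YSI values that is enough to settle agreement. Setting such a pair aside as if nothing were known removes a certain failure from the denominator of 1a, and can do so for 1b and 1c. It also removes a large ARD from 1d.

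Success requires all four criteria on the available pairs, and no sensitivity result enters that rule. The determinable misses therefore never reach the pass/fail decision. In the best-case sensitivity analysis the same known misses are scored as agreement.

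**Working it through.** **1. Which Low/High pairs are certain 20/20 misses** (agreement as defined in SAP 5.2)

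- Low, true value below 40. For YSI from 60 to 80 the difference exceeds 60 − 40 = 20 mg/dL. For YSI above 80 the relative deviation exceeds (80 − 40)/80 = 50%. So every Low with YSI of 60 or more is a miss.
- High, true value above 400. Agreement needs a value of at most 1.2 × YSI, and 400/1.2 = 333.3. So every High with YSI of 333 or less is a miss.
- ARD floors: Low at YSI 60, 20/60 = 33.3%; Low at YSI 100, 60%; High at YSI 250, 150/250 = 60%; High at YSI 333, 67/333 = 20.1%. Every certain miss thus has an ARD above the 20% MARD threshold.

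**2. The plan's own figures** (SAP 6.2; one-sided 0.025; z = 1.96 and 0.845)

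- 1a: [1.96√(0.6×0.4) + 0.845√(0.65×0.35)]²/0.05² = 743.4, so 744 points.
- 1b/1c: the same formula with 0.90 and 0.95 gives 238.5, so 239 points.
- 1d: (1.96 + 0.845)² × 25/4 = 49.2, so 50 subjects.
- Power at 1,200 points is 94.7% (1a) and above 99.9% (1b/1c). At 60 subjects it is 87.3% by the normal formula (1d). The stated power claims reproduce, with points treated as independent.

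**3. Shift in the estimates.** The documents give no Low/High rate, so the counts below are assumptions. Take 24 dropped pairs beside 1,200 retained at the planning rates.

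- 1a, all 24 misses: 780/1,200 = 65.0% against 780/1,224 = 63.7%, an overstatement of 1.27 points.
- 1b/1c, all 24 outside A+B: 1,140/1,200 = 95.0% against 1,140/1,224 = 93.1%, an overstatement of 1.86 points.
- All 24 agreeing instead: 804/1,224 = 65.7% and 1,164/1,224 = 95.1%. The sign reverses, to −0.69 and −0.10 points.

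**4. Dropped misses needed to reverse a pass at the planning rates.** Add k misses to the denominator until the 97.5% lower limit is no longer above the threshold.

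- 1a: k = 45 by the normal approximation (780/1,245, limit 59.96%) or 43 by Clopper-Pearson (780/1,243). That is 3.6% or 3.5% of pairs.
- 1b/1c, dropped pairs outside A+B: k = 46 (1,140/1,246, limit 89.94%) or 44 (1,140/1,244, limit 89.96%). That is 3.7% or 3.5%.

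**5. False-pass chance with the true rate at the null.** A share f of 1,200 pairs consists of dropped misses. The retained number is 1,200(1 − f) and the retained rate is p0/(1 − f). The chance is the exact binomial probability that the lower limit exceeds p0.

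| f | 1a normal / exact | 1b or 1c normal / exact, dropped pairs outside A+B |
|---|---|---|
| 0 | 2.7% / 2.4% | 3.5% / 2.2% |
| 0.5% | 4.0% / 4.0% | 9.0% / 6.1% |
| 1% | 6.5% / 5.7% | 23% / 17% |
| 2% | 13.4% / 13.4% | 61% / 57% |
| 5% | 61% / 59% | about 100% |

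**6. MARD.** Suppose the retained MARD is 18% and 2% of pairs, with ARD 60%, are restored evenly over subjects: 0.98 × 18 + 0.02 × 60 = 18.84%. With SD 5 (held fixed) and 60 subjects, the largest mean that passes is 20 − 2.001 × 5/√60 = 18.71%.

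**The case against.** **Agreeing pairs are dropped too.** The rule also removes Low readings beside a truly very low YSI and High readings beside a very high one. Protocol 9.9.1 samples every 5 minutes below 75 mg/dL, and Protocol 9.12.1.1 sets a glucose target around 70 mg/dL, so low-range pairs are to be expected. This stands. A reader might infer that the pass/fail decision as a whole is biased in the device's favour. The documents do not support that, because the net direction depends on a mix of hits and misses that they do not report.

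**A 20/20 miss need not lie outside Zone A+B.** The Clarke description in SAP 7.8 puts pairs where both methods indicate hypoglycaemia in Zone A, and harmless disagreement above 20% in Zone B. This stands. The 1b/1c figures above are the extreme in which every dropped pair is outside A+B.

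**Planning rates leave a margin.** A reader might infer that a loss of 1 to 2% would overturn the result. At the planning rates it would not. With 2% lost, 764/1,176 becomes 764/1,200 = 63.7% (exact limit 60.9%), and 1,117/1,176 becomes 1,117/1,200 = 93.1% (exact limit 91.5%). Both still pass. The effect matters when performance is near a threshold.

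**The plan already covers it.** The 40–400 range is pre-specified, and the worst case is harsher than scoring the pairs correctly. Both statements are true, but pre-specification does not make a known outcome unknown. The *or* in the range sentence, read literally, excludes no value. The worst case does not decide success and mixes these readings with missed YSI draws. The analysis sentence in SAP 7.7 names only the three rates, not MARD. A best case is meant to be optimistic about what is unknown, and a certain miss is not unknown.

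**Conclusion.** The point holds in a limited form. Under SAP 6.6.1 and 7.6, Low/High readings leave all four primary endpoints, including pairs that are certain 20/20 misses. For those pairs the direction is certain for 1a. It holds for 1b/1c when the pair is also outside Zone A+B. For 1d the high ARD floor means that dropping them lowers MARD in general.

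The size is unknown because no Low/High rate is given. About 3.5% of pairs would have to be dropped misses to reverse a pass at the planning rates. With the true rate at the null, 2% raises the 1a false-pass chance from about 2.5% to about 13%. These figures assume 1,200 pairs and independence between pairs, as the SAP does; clustering within subjects would change the probabilities but not the direction. The change should be made before the analysis is run, but the documents do not show that the trial's conclusion would differ.

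**What to change.** - **SAP 6.6.1, 6.6.2 and 7.6:** use SBG to identify Low/High readings that pair with a YSI value. Include them in 1a–1c wherever the bound (below 40 or above 400) settles agreement or the error-grid zone. Count certain 20/20 misses as No, and read zones from the grid rather than assuming that they are outside A+B.
- **Undecided pairs:** do not substitute 40 or 400 and accept the result. Low at YSI 55 with a true 30 is a miss by 25 mg/dL, but 40 scores it as a 15 mg/dL hit. High at YSI 350 with a true 450 is a miss at 29%, but 400 scores it as a 14% hit. Low at YSI exactly 60 is a certain miss, but 40 gives exactly 20. Report results with undecided pairs scored both ways; adding back only the certain misses would tilt the other way.
- **1d:** use 40 or 400 as a floor on the ARD only when YSI is at least 40 (Low) or at most 400 (High). Outside that it is not a floor: YSI 30 with a true 30 has ARD 0, but 40 gives 33%.
- **SAP 6.5:** take determinable Low/High pairs out of the missing cases, so that the best case cannot score a known miss as agreement.
- **Reporting:** tabulate Low/High counts by YSI range, keep the SG-only result as secondary, and change *or* to *and* in the 40/400 sentence.

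SBG is already downloaded, so the cost is SAP wording, minor programming and possibly slightly less favourable rates.
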